9.4. Data sources

RCC Registry will be used as the sole data source for this study.

For this purpose, no Case Report Forms (CRFs) or Data Collection Tools (DCTs) will be utilized, but the RCC Registry database will be used directly. Eligible patients' data will be anonymized and extracted for analysis by the registry owner, for this study.

The RCC Registry was approved by Ankara University Ethical Committee in October 2018 and by Ministry of Health in March 2019.

9.5. Study size

In the scope of the study, RCC Registry will be screened for all patients who meets all inclusion criteria and who doesn't meet the exclusion criterion defined in the study protocol and who were treated with Sunitinib in first-line therapy for mRCC and were registered to the database between 2019 and 2022.

The annual disease burden in contributing centers to RCC Registry is approximately 100 patient/center, the treatment of an average of 250 patients per year is continued in the centers. Therefore, it is planned to include the information of approximately 400 patients whom records were registered in between 2019 and 2022 and who meet the patient selection criteria.

9.6. Data management

The below data in Registry database will be anonymized by registry administrators.

- Variables to be obtained from the Registry : Demographic information (age, sex), physical measurements (height and weight measurements), disease and concomitant disease history (Hypertension, Diabetes mellitus), previous treatments (ACE-I / ARB, statin), age of start of Sunitinib, smoking history, date of diagnosis, surgery type (Radical nephrectomy, partial nephrectomy), histopathological information and other involvement information, treatment given (order of treatment given, starting date, dose, dose changes, if available), discontinuation of treatment information and the reason, previous IFN use, toxicities leading dose reduction and treatment discontinuation, information of risk (IMDC, MSKCC subgroups), performance scores, metastasis site information, laboratory values, if available, survival status .
- This anonymized data will be transferred to the clinical database of the study in Omega CRO.
- Omega CRO will analyze this anonymized data and provide the results to Pfizer.

No individual anonymized patient data will be provided to Pfizer.

9.7. Data analysis

The Statistical Package for Social Sciences (SPSS) 19.0 for Windows will be used for the analysis. A type-I error of less than 5% will be interpreted as statistically significant.

Normality of data will be tested using the visual (histogram and probability plots) and analytical (Kolmogorov-Smirnov/Shapiro-Wilk tests) methods. Descriptive statistics will be expressed as numbers and percentages for categorical variables and as mean and standard deviation for normally distributed numerical variables, median and interquartile range (IQR) for non-normally distributed numerical variables. For Survival Analyses, Kaplan-Meier estimates will be calculated and for survival rate comparison of Kaplan-Meier estimates within selected categorical groups will be investigated using log rank test.

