8. RESEARCH QUESTION AND OBJECTIVES

The purpose of this study is to observe the treatment response in patients with mRCC treated with Sunitinib in first-line therapy.

Primary Objective:

- Evaluation of Sunitinib treatment responses/objective response rate according to disease risk group in patients with mRCC treated with Sunitinib in first-line therapy in Turkey

Secondary Objectives:

- Evaluation of survival and treatment response to Sunitinib treatment regimen
- Determination of factors affecting the treatment regimen change and the frequency of these factors in patients with mRCC
- Determination of demographic, clinical and pathological characteristics of patients with mRCC
- Determination of median duration use of patients using IFN.

[figure not shown]

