9. RESEARCH METHODS

9.1. Study design

This study is a non-interventional, retrospective, evaluational study based on data extracted and analyzed from the RCC Registry.

This study was designed to answer the Sunitinib treatment responses/objective response rate according to disease risk group in patients with mRCC.

PFIZER CONFIDENTIAL

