9.2. Setting

Analysis for this study will be conducted on data anonymized and extracted from RCC Registry; time frame for this study data set is information of eligible patients that were registered in RCC Registry between March 2019 and October 2022.

RCC Registry is a data log where clinical information is recorded by inviting patients who meet the patient selection criteria according to registry protocol from 6 different centers since March 2019. In this study, RCC Registry will be used as sole data source.

The annual disease burden in contributing centers to RCC Registry is approximately 100 patient/center, the treatment of an average of 250 patients per year is continued in the centers. Therefore, it is estimated that information of approximately 400 eligible patients who were registered in RCC Registry from 2019 to 2022 will be included in the analysis.

Study Schedule GES / Timeline	November 2022	December 2022	January 2023	February 2023	March 2023	April 2023
Preparation phase and obtaining necessary approvals	X	X				
Extracting data from RCC Registry			X	X		
Data management, statistical analysis and reporting				X	X	X

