9.3. Variables

The following variables will be extracted from RCC Registry in the scope of this study:

- Demographic information (age, sex)
- Physical measurements (height and weight measurements)
- Disease and concomitant disease history (Hypertension, Diabetes mellitus)
- Previous treatments (ACE-I / ARB, statin)
- Age of start of Sunitinib,
- Smoking history,
- Date of diagnosis
- Surgery type (Radical nephrectomy, partial nephrectomy)
- Histopathological information
 - Pathological type,
 - Pathological stage and location,
 - T size and location
 - Fuhrman Grade,
 - Adrenal involvement,
 - Lymph node (LN) involvement,
 - Number of LNs removed,
 - Sarcomatoid feature,

- Other involvement information
- Treatment given (order of treatment given, starting date, dose, dose changes, if available)
- Discontinuation of treatment information and the reason
- Previous IFN use
- Toxicities leading dose reduction and treatment discontinuation
- Information of risk (International Metastatic RCC Database Consortium (IMDC), Memorial Sloan Kettering Cancer Center (MSKCC) subgroups)
- Performance scores (ECOG)
- Metastasis site information
- Laboratory values, if available
- Survival status

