9.9. Limitations of the research methods

Limitation in this study is defined as not to reach enough patients data for statistical analysis.

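### The primary objective is ORR by risk group, but the plan lists no response variable and no confidence interval, so it yields either no ORR or bare percentages

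*Combined protocol and SAP*

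**What the plan says.** Section 8 gives the primary objective as the evaluation of "treatment responses/objective response rate according to disease risk group in patients with mRCC treated with Sunitinib". Section 9.1 repeats it as the purpose of the design: "This study was designed to answer the Sunitinib treatment responses/objective response rate according to disease risk group in patients with mRCC".

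Section 9.7, repeated in the abstract, is the only analysis text, and Annex 1 lists no stand-alone document that could add to it. It covers software, a 5% significance threshold, normality checks, summaries by type of variable, and Kaplan-Meier estimates with a log-rank test. For categorical data the rule is: "Descriptive statistics will be expressed as numbers and percentages for categorical variables". The one comparison between groups concerns survival: "survival rate comparison of Kaplan-Meier estimates within selected categorical groups will be investigated using log rank test".

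Sections 9.3 and 9.6 list what will be extracted. Risk group is there (in 9.6, "information of risk (IMDC, MSKCC subgroups"), as are treatment given, discontinuation and its reason, toxicities and survival status. Best response, response category and response criteria are not. Section 9.4 makes the registry the sole source and rules out case report forms and other collection tools.

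On size, 9.2 forecasts "approximately 400 eligible patients who were registered in RCC Registry from 2019 to 2022 will be included in the analysis". Section 9.9 gives one limitation: "Limitation in this study is defined as not to reach enough patients data for statistical analysis".

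**The concern.** The primary question and the analysis plan do not meet. Two links are missing.

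- **The data.** ORR needs a response outcome for each patient, and neither extraction list contains one. Discontinuation reasons and survival status do not show whether a tumour responded.
- **The estimate.** If response is extracted after all, 9.7 asks only for a count and a percentage. A descriptive study needs no hypothesis test of ORR, but an estimate should come with its uncertainty. The objective is stated per risk group, where numbers are smaller than the total of about 400.

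Without intervals, a gap between risk groups that chance could easily produce may be read as a real difference in response.

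**Working it through.** **Step 1: trace the primary objective through the plan.**

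| Needed for ORR by risk group | Where it would be | Found? |
|---|---|---|
| Risk group | 9.3, 9.6 | Yes |
| Response per patient | 9.3, 9.6 | No |
| Denominator and handling of non-evaluable responses | 9.7 | No |
| Summary rule for a yes/no outcome | 9.7 | Only the general rule: count and percentage |
| Confidence interval | anywhere | No |

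**Step 2: inputs for the illustration.** The plan gives about 400 patients (9.2, 9.5). That figure rests on patient volume, with no expected ORR, effect size or precision target, so there is no precision figure to reproduce. The documents give no expected ORR and no risk-group sizes. I assume an ORR of 20%, 30% or 40%, and group sizes of 133 (400/3, three equal groups), 100, 80 and 40.

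**Step 3: precision of one ORR.** With x responders out of n, the exact (Clopper-Pearson) 95% limits are the 2.5% point of Beta(x, n-x+1) and the 97.5% point of Beta(x+1, n-x). The half-width is half the distance between them.

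| n | ORR about 20% | ORR about 30% | ORR about 40% | Half-width (points) |
|---|---|---|---|---|
| 400 | 80/400: 16.2-24.3% | 120/400: 25.5-34.8% | 160/400: 35.2-45.0% | 4.0-4.9 |
| 133 | 27/133: 13.8-28.1% | 40/133: 22.4-38.6% | 53/133: 31.5-48.7% | 7.2-8.6 |
| 100 | 20/100: 12.7-29.2% | 30/100: 21.2-40.0% | 40/100: 30.3-50.3% | 8.3-10.0 |
| 80 | 16/80: 11.9-30.4% | 24/80: 20.3-41.3% | 32/80: 29.2-51.6% | 9.3-11.2 |
| 40 | 8/40: 9.1-35.6% | 12/40: 16.6-46.5% | 16/40: 24.9-56.7% | 13.3-15.9 |

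Hand check for 40/100: 1.96 × √(0.4 × 0.6/100) = 9.6 points, close to the exact 10.0. Wilson half-widths are a little smaller: 3.9-4.8, 6.8-8.2, 7.8-9.4, 8.7-10.5 and 12.1-14.5 points, in the same order of n.

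**Step 4: precision of a difference.** The Newcombe interval combines the Wilson limits (l, u) of each group: lower = d - √[(p1-l1)² + (u2-p2)²] and upper = d + √[(u1-p1)² + (p2-l2)²]. For 40/100 against 30/100, the Wilson limits are 30.9-49.8% and 21.9-39.6%.

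- Lower: 10 - √(9.1² + 9.6²) = 10 - 13.2 = -3.2 points.
- Upper: 10 + √(9.8² + 8.1²) = 10 + 12.7 = 22.7 points.

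The same formula for 32/80 against 24/80 gives 10 points (-4.7 to 24.1).

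**Step 5: how often chance alone gives a 10-point gap.** Give two groups the same true ORR and sum the product of the two binomial probabilities over all outcomes whose observed rates differ by at least 10 points.

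| Per group | ORR 20% | ORR 30% | ORR 40% |
|---|---|---|---|
| 133 | 3.8% | 7.1% | 9.1% |
| 100 | 9.3% | 14.2% | 17.0% |
| 80 | 13.8% | 19.5% | 22.6% |

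At 133 per group the smallest qualifying gap is 14 responders (14/133 = 10.5 points), which accounts for part of the drop from 100 per group.

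**The case against.** The strongest reply is that the study is descriptive and has one treatment, so a count and percentage per risk group is an adequate analysis. Any reader can derive an interval from n/N. The omission biases no estimate. This stands in part: no test of ORR is needed, and a reader might wrongly infer that 9.7 contains no analysis at all for the primary objective. The general rule for categorical variables does cover a yes/no response. What does not stand is that this is enough. The plan does not commit to reporting precision, and a reader cannot recover a denominator that was never defined.

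A second reply is that the size of the problem depends on assumed group sizes. That is correct. With three equal groups of about 133, a chance gap of 10 points or more occurs in only about 4-9% of studies. Groups may well be unequal, however, so the range is shown.

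Four stronger readings are tempting, and the documents do not support them:

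- **The registry holds no response data.** The documents show only that response is absent from the extraction lists. They do not say what else the registry records.
- **Section 9.9 admits imprecise estimates.** It says only that enough patients' data may not be reached, which concerns availability.
- **About 400 patients is too few.** No precision target is stated against which to judge that number.
- **Two risk systems and unnamed log-rank groups invalidate the primary analysis.** These are missing details. ORR could be tabulated under both systems, and the log-rank test concerns survival, a secondary objective.

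**Conclusion.** The point holds in this form: the plan names ORR by risk group as its primary objective, lists no variable from which to compute it, and plans no interval for it. The result would be no ORR, or percentages without stated precision.

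The textual gap needs no assumption. Its numerical weight does: the half-widths and chance-gap rates rest on assumed ORRs and group sizes, with only the total of about 400 taken from the plan. Under those assumptions the overall ORR is known to within about 5 points, while a risk group of 40 to 133 is known only to within about 7 to 16.

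The change should be made before extraction. Intervals would describe sampling error only. They would not cover selection arising from 9.2.2, which removes patients who started treatment and then left follow-up.

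**What to change.** 1. **Before extraction, confirm that the registry records best overall response.** If it does, add it to the lists in 9.3 and 9.6. If it does not, the primary objective cannot be met from this sole source and must be restated.
2. **In 9.7, name ORR as the primary analysis.** Report it overall and per risk group as n/N with a 95% CI (Clopper-Pearson or Wilson). State who is in N and how non-evaluable responses are counted.
3. **Give any contrast between risk groups as a difference with a 95% Newcombe CI.** No test needs to be added.
4. **State in 9.9 that the intervals do not reflect selection from the follow-up exclusion in 9.2.2.**

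If response is recorded, the cost is one added item in each list, a few sentences in 9.7 and 9.9, and a few lines of analysis, with no extra patients. The downside is that wide intervals in small risk groups will be visible. If response is not recorded, the cost is larger, because the objective itself has to change.

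### Survival comparisons by any factor other than risk group rest on an unadjusted log-rank test, so a significant result may only reflect a different risk-group mix

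*Combined protocol and SAP*

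**What the plan says.** The survival objective in section 8 is secondary: "Evaluation of survival and treatment response to Sunitinib treatment regimen". Section 9.7, repeated in the abstract, serves it with Kaplan-Meier estimates and one comparative method: "survival rate comparison of Kaplan-Meier estimates within selected categorical groups will be investigated using log rank test". The same section sets the decision rule: "A type-I error of less than 5% will be interpreted as statistically significant".

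The groups to be compared are not listed. No Cox model, stratified test, covariate list or hazard ratio appears anywhere, and Annex 1 lists no stand-alone document that could supply them.

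Section 9.3 extracts the IMDC and MSKCC risk subgroups, ECOG score and age. It also extracts many variables that could serve as grouping factors, including surgery type, pathological type, sarcomatoid feature, previous IFN, ACE-I/ARB and statin use, smoking and metastasis site. Section 9.9 gives one limitation, too few patients, and does not mention confounding.

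**The concern.** All patients receive sunitinib, so no treatments are compared. Any survival comparison is between patient groups in a registry cohort, and such groups may differ in prognosis for reasons unrelated to the factor that defines them. The protocol itself treats disease risk group as central, because the primary objective reports response by it. The survival analysis never uses it for adjustment.

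Suppose a factor is more common in one risk group than another. The crude log-rank test then picks up the survival difference between risk groups and reports it under the factor's name. With a 5% rule attached, the result will be read as a finding about the factor. A log-rank p-value also says nothing about how large the difference is.

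Timing matters. Under section 9.6 the CRO analyses the data and the sponsor receives results only, not patient-level data. The sponsor could not fit an adjusted model itself afterwards, and covariates chosen once results are known would be open to question.

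**Working it through.** **1. The plan's own figure.** The only planning number is the study size: "it is planned to include the information of approximately 400 patients whom records were registered in between 2019 and 2022". Its stated basis is "approximately 100 patient/center, the treatment of an average of 250 patients per year is continued in the centers", with patients recruited "from 6 different centers since March 2019". The window in section 9.2, March 2019 to October 2022, is 44 months.

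- 250 per year × 44/12 = 917; 400/917 = 44%.
- 100 × 6 centres × 44/12 = 2,200; 400/2,200 = 18%.

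Neither gives 400 without an eligible share that is not stated, so 400 is neither confirmed nor shown wrong. It is used below only as the simulated cohort size. No event count, hazard ratio or power is given, so there is no survival calculation to reproduce.

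**2. Design of the check.** A binary factor is given a true hazard ratio (HR) of 1 within every risk group. Each scenario has 2,000 simulated studies of 400 patients, exponential survival and two-sided 5% tests (the plan does not state sidedness). The crude log-rank test is compared with the log-rank test stratified by risk group. All rates, mixes and prevalences are assumptions.

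**3. First set of assumptions.** Factor present in half the patients, median survival 24 months at intermediate risk, uniform censoring at 3 to 47 months, about 200 deaths. Mixes are favourable/intermediate/poor.

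| Hazards | Mix with factor | Mix without factor | Crude | Stratified |
|---|---|---|---|---|
| 1 : 1.7 : 3.4 | 25/55/20% | 15/55/30% | 13.2% (HR about 0.89) | 5.1% |
| 1 : 1.7 : 3.4 | 30/55/15% | 15/50/35% | 32.4% (HR about 0.81) | 5.8% |
| 1 : 1.4 : 2.2 | 25/55/20% | 15/55/30% | 8.9% | 5.3% |

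A small imbalance gave 6.9% crude and 5.3% stratified. No imbalance gave 4.8% and 5.1%. A repeat run put the strong-imbalance row at 33%. The simulation standard error there is √(0.324 × 0.676/2,000) = about 1 percentage point.

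**4. Check by formula.** The expected log-rank statistic is about |ln HR| × √(d·p·(1−p)), where d is deaths and p is factor prevalence. The rejection rate is Φ(z − 1.96) + Φ(−z − 1.96).

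- HR 0.89, d = 200, p = 0.5: z = 0.1165 × √50 = 0.82, rejection 13%.
- HR 0.81, d = 200, p = 0.5: z = 0.2107 × √50 = 1.49, rejection 32%.

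Both agree with the simulation.

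**5. Second set of assumptions.** Risk mix 25/50/25%, median 30 months at favourable risk, uniform censoring at 3 to 44 months, about 208 to 251 events. The columns give factor prevalence in the favourable/intermediate/poor groups; the cells give the crude rejection rate and apparent HR.

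| Risk-group hazards | 30/40/50% | 20/40/60% | 15/40/70% |
|---|---|---|---|
| 1/1.5/2.25 | 8% (1.08) | 21% (1.18) | 35% (1.26) |
| 1/2/4 | 19% (1.15) | 56% (1.33) | 80% (1.46) |
| 1/2/6 | 27% (1.19) | 72% (1.40) | 94% (1.60) |

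With equal prevalence (40/40/40%) the crude test rejects 4.2% to 4.8%. The stratified test stays between 4.1% and 5.9% throughout, with an average HR of 0.995 to 1.006. With 200 patients, hazards 1/2/4 and prevalence 30/40/50%, the crude rate is 10% against 4.5% stratified.

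The Cox model was not run. It is the regression counterpart of the stratified test.

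**The case against.** **The stronger reading.** A reader might infer that every survival comparison in the plan is confounded. The documents do not support that. The only grouping named in an objective is disease risk group, and for survival by risk group the crude log-rank test is a valid descriptive contrast.

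**The plan makes no claim about other factors.** It never says survival will be compared by statin use, smoking, nephrectomy or previous IFN. These are extraction variables, and the objective about factors concerns change of treatment regimen. No independent or causal effect is claimed. If the risk mix differs, survival really does differ between the groups, and the crude test correctly rejects its own null hypothesis. The error lies in reading the result as the factor's effect. This stands and narrows the point. It does not remove it, because the groups are left open, a significance rule is attached and no warning about confounding is given.

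**The size is assumed.** The documents give no risk mix, hazards, event count or link between any factor and risk group. This also stands. The direction is the same in every linked scenario, but no single figure can be assigned to this study.

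**Adjustment may not be free or complete.** A reader might infer that the extracted data would have removed the confounding. That is not established. Completeness of risk group is unknown, laboratory values come only if available, and unmeasured differences would remain. The extraction list names survival status but no explicit date of death or last contact. Kaplan-Meier and Cox analyses both need such a date.

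**Labelling alone might do.** Calling the results unadjusted and listing confounding would prevent the misreading. It would still leave no adjusted estimate and no effect size for any factor the report discusses.

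**Conclusion.** The point holds for comparisons by factors other than risk group. There, section 9.7 offers only a test that cannot separate the factor from a difference in risk-group mix, and it reports no effect size. Under the first set of assumptions, a factor with no effect within risk groups is called significant about 7% to 33% of the time for small to strong imbalance. Across the second set the range is 8% to 94%. The rate is about 5% when the factor is unrelated to risk group or when the test is stratified.

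These figures rest on assumed mixes, hazards and roughly 200 to 250 events, none of which is in the documents. The mechanism does not depend on the figure of 400. Survival is a secondary objective and the primary response objective is untouched, so this should be changed but does not undermine the study as a whole.

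**What to change.** In section 9.7:

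- Name the groups in which survival will be compared.
- Keep Kaplan-Meier curves and log-rank tests, labelled as unadjusted description. This is sufficient for comparisons by risk group.
- For any other factor, base statements about survival on a log-rank test stratified by IMDC (or MSKCC) risk group, or on a Cox model with risk group and age. State in advance which risk score is used, and report the adjusted hazard ratio with its 95% CI (a stratified Cox model supplies it if the stratified test is chosen).
- Add further covariates only if they are sufficiently complete and the event count allows. Be cautious with those recorded only in operated patients, such as number of lymph nodes removed, because complete-case fitting would drop unoperated patients.
- Report how many patients lack a risk group.

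In section 9.9, list residual confounding. Confirm with the registry owner that the dates needed for time-to-event analysis will be in the extract.

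The cost is a few lines of text, one extra model per factor, and the loss of patients with missing risk group from the adjusted analyses. No additional patients are needed.
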